**Evaluation of an Incentive-based Intervention to
Improve 90-day Adherence in PAP-Naïve Patients:
Project Dahlia**

Investigational Plan

Version: **2.0**

Date: **08Jul2019**

Protocol Number: **SLP-18-08-01**

Sponsor: **ResMed Corp**
[name]
[name]
[contact]

NCT Number: **NCT03851094**

This protocol has been written in accordance with current applicable guidelines (IDE for USA) as well as all other relevant additional references, medical and legal.

The information herein is confidential and the property of ResMed Corp. It is to be used in confidence for the conduct of the clinical trial according to written agreement.

Version History

Version	Date	Notes
1.0	10Jan2019	Original Version
2.0	08Jul2019	Removed inclusion criteria for patients to have used their device less than an average of 3.5 hours of usage in the first 3 days of therapy.

Protocol Summary

Study Design:	
This is a prospective, randomized, open-label study to evaluate effectiveness of applying financial and social incentives via a smartphone-based app in helping participants achieve adherence to therapy. Randomization will consist of an allocation ratio of 2:1 (control:treatment)
 
This study will be conducted on patients with obstructive sleep apnea (OSA) who have been prescribed ResMed flow generator for positive airway pressure (PAP).
 
Participants will be randomized to one of two groups: control or intervention with Wellth app, "Restful". The study comprises up to 2 participant contacts by phone, and 3 data collection timepoints. The first contact involves consenting and enrolling the participant, providing instructions based on the arm they are randomized to, and collecting baseline data including questionnaires. Those randomized to the intervention group will have a second contact, which involves onboarding to Restful. A second administration of the questionnaires will occur at +90 days from baseline.

Intervention:	
Restful by Wellth. The intervention is use of the Restful app, which provides a small daily financial reward for achieving therapy usage goals and social support. The app will also send a daily reminder to participants to use their therapy. There is no clinical treatment intervention, as all patients included in this trial will be receiving PAP therapy per standard of care.

Objectives:	
Evaluate whether a digitally delivered monetary and social reward scheme can increase 90-day adherence and/or increase average minutes of therapy usage over time. Therapy usage will be monitored using cloud-based technology in which data from each PAP device is automatically transmitted to a secure, HIPAA-compliant system (AirView).

Enrollment:	Up to 300 participants
Clinical Site(s):	1 - 2 sites
Patient Population:	The intended population for the study are patients with a new diagnosis of OSA who have been prescribed a ResMed flow generator compatible with AirView. Participants will be recruited from the site's database.
Endpoint:	Adherence to therapy (average hours per day) at 90-days

Duration of study: Each participant is expected to participate in the study for at least 90 days following enrollment. Enrollment completion is expected within 16 weeks of enrollment initiation. Participants' usage data will also be collected at 180 days following enrollment.

TABLE OF CONTENTS

1	INTRODUCTION	6
2	OBJECTIVES	7
3	METHODS AND MATERIALS.....	7
3.1	POPULATION/PARTICIPANT SELECTION.....	7
3.2	STUDY DESIGN.....	7
3.3	NUMBER OF PARTICIPANTS.....	8
3.4	INCLUSION CRITERIA.....	8
3.5	EXCLUSION CRITERIA.....	8
3.6	SAMPLE SIZE.....	8
3.7	STUDY ENDPOINTS.....	9
3.8	ANALYSIS POPULATIONS.....	9
3.9	DATA ANALYSIS.....	9
4	STUDY SCHEDULE	10
4.1	SCREENING FOR ELIGIBLE PARTICIPANTS:.....	11
4.2	INITIAL (ENROLLMENT) CONTACT	11
4.3	90-DAY STUDY CONTACT.....	11
4.4	REPORT OF DEVICE USAGE DATA.....	11
4.5	STUDY FLOW	12
4.6	INFORMED CONSENT.....	13
5	INTERVENTION.....	13
5.1	WELLTH APP (RESTFUL).....	13
5.2	AIRVIEW	14
5.3	MYAIR	15
5.4	CONTROL GROUP	15
6	DATA HANDLING AND RECORD KEEPING	15
6.1	CONFIDENTIALITY	15
6.2	SOURCE DOCUMENTS	15
6.3	CASE REPORT FORMS.....	15
6.4	RECORDS RETENTION	16
7	MONITORING	16
8	ADVERSE EVENT REPORTING.....	16
9	EXPECTED ADVERSE DEVICE EFFECTS	17
10	NON SIGNIFICANT RISK DETERMINATION	17
11	RISK MITIGATION.....	17
12	REFERENCES	18
APPENDIX A: PARTICIPANT QUESTIONNAIRES.....		20
APPENDIX B: TAKE HOME INSTRUCTIONS.....		21
GROUP A	21	
GROUP B	22	
APPENDIX C: MYAIR PRIVACY POLICY	23	
APPENDIX D: WELLTH PRIVACY POLICY	31	

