1 INTRODUCTION

Obstructive Sleep Apnea (OSA) is a condition characterized by the partial or complete collapse of the upper airway during sleep. OSA comprises a continuous spectrum of severity ranging from simple snoring and upper airway resistance through mild to severe symptomatic obstructive hypopnea and apnea. The prevalence of sleep disordered breathing in the adult population is 24% males and 9% for females¹. The prevalence of symptomatic OSA in the adult population has been estimated to be 4% in males and 2% in females¹. These patients demonstrate behavioral and neuropsychological consequences to varying degrees, including excessive daytime sleepiness, intellectual deterioration and depression². More serious consequences include arterial systemic hypertension, arterial pulmonary hypertension and heart disease³.

The treatment of choice for OSA is Positive Airway Pressure (PAP). PAP acts as a positive airway splint, delivering a fixed positive airway pressure to the upper airway via a tube and mask. Humidification is used during PAP therapy to improve comfort of the delivered air and alleviate nasal dryness/congestion.

Although PAP therapy is the gold standard treatment for OSA, adherence to treatment is often poor. CMS guidelines define adherence as 4 or more hours per night of therapy use on 70% of nights during a consecutive 30-day window within the first 90 days of setup⁴. Anywhere from 30 to 85% of patients will be non-adherent according to this definition of adherence, which can be explained, in part, by factors such as socioeconomic status, age, gender, severity of presenting symptoms, health values/beliefs, and social support⁵. Importantly, patients who immediately adopt therapy, within the first 3 days, are significantly more likely to be adherent at 30 days⁶, and patients' usage at 1 month is significantly predictive of adherence at 1 year⁷. Without sustained, long-term therapy adherence, patients are at risk of negative health outcomes including but not limited to cardiovascular disease, stroke, diabetes, and depression. This study tests whether a combined financial plus social incentive can help users new become adherent to PAP therapy.

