3.4 INCLUSION CRITERIA

All Participants enrolled into the study must meet the following criteria for entry:

- Adult participants (≥ 18 years of age)
- New diagnosis of OSA
- Prescribed CPAP or APAP for treatment of OSA
- Prescribed a ResMed flow generator compatible with AirView
- Owns a smart phone and is willing to download an app on their phone
- Willing and able to give informed consent
- Can read and comprehend written and spoken English

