3.8 ANALYSIS POPULATIONS

Randomized Population: all participants enrolled and randomized to treatment groups.

Intent-to-Treat (ITT) Population: all participants randomized to control or intervention group, regardless of the actual intervention received.

Evaluable Population: all ITT subjects who complete the 90-day study period and complete the end-of-study questionnaire.

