3.9 DATA ANALYSIS

Baseline demographic and psychosocial factors will be summarized for each randomized group for ITT and Evaluable Populations. For continuous variables, such as age and PAP usage, the mean, standard deviation, median, and range will be presented. For categorical variables, such as gender, the number and proportion of participants in each category will be presented. Baseline demographics and psychosocial factors for the control and intervention groups will be compared with t-tests and Fisher's exact tests, as appropriate.

The primary analysis compares mean PAP usage at 90 days in the control and intervention groups using a two-way ANOVA on the ITT population. Randomization group and myAir usage (Yes/No) will be included as factors in the model. The interaction of the two factors will be considered, but will only be retained in the model if it is significant at the 5% level. Missing usage hours during a day will be imputed as 0 usage. A secondary analysis of mean PAP usage will be conducted using the Evaluable Population. A sensitivity analysis of the missing data assumption will be conducted by considering missing data as missing. In this analysis, participants with no usage data will be assumed to have a mean usage of 0 hours; other participants' mean usage will be calculated as the mean usage across nights for which there is data.

A subgroup analysis of the primary endpoint will be generated for patients who are identified as strugglers. A struggler is defined as a patient who uses their device for less than or equal to 3.5 hours/night during the first 3 days of usage. Mean PAP usage at 90 days will be compared in the control and intervention groups using a two-way ANOVA on the struggler population as described above. Descriptive statistics will also be presented for mean PAP usage, comparing strugglers and non-strugglers in control and intervention groups.

Adherence will be calculated for the ITT population from daily usage data using the Medicare definition for adherence (a patient is adherent if they use the device for more than 4 hours per night for 70% of the nights during the first 90 days of usage). Percent adherence will be compared between control and intervention groups using a logistic regression model on the ITT population. Randomization group, myAir usage, and the interaction of these two factors will be included in the model. Missing usage hours during a day will be imputed as 0 usage.

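### If anyone was randomised under version 1.0, the Section 3.9 models leave out protocol version, a probably prognostic factor fixed before randomisation; the cost is precision and interpretability, not bias

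*Combined protocol and SAP*

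**What the plan says.** The Version History dates version 1.0 to 10Jan2019 and version 2.0 to 08Jul2019. The note on version 2.0 reads: "Removed inclusion criteria for patients to have used their device less than an average of 3.5 hours of usage"; the period concerned is the first three days of therapy. The current list in Section 3.4 has no early-usage requirement; it asks, among other things, for "Prescribed CPAP or APAP for treatment of OSA".

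Section 3.8 defines the ITT population as "all participants randomized to control or intervention group, regardless of the actual intervention received". Section 3.9 then states: "The primary analysis compares mean PAP usage at 90 days in the control and intervention groups using a two-way ANOVA on the ITT population". On the model terms it says "Randomization group and myAir usage (Yes/No) will be included as factors in the model", with their interaction kept only if significant at 5%. The logistic model for adherence uses the same two factors and their interaction. Neither model has a term for protocol version, enrolment period or early usage, and Sections 3.2 and 4.2 describe no stratified randomisation.

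Section 3.9 also plans a separate ANOVA in strugglers and descriptive statistics for strugglers and non-strugglers by arm. The definition, which counts days from the start of device use, is "A struggler is defined as a patient who uses their device for less than or equal to 3.5 hours/night during the first 3 days of".

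On the relevance of early use, Section 1 says that "patients who immediately adopt therapy, within the first 3 days, are significantly more likely to be adherent at 30 days".

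**The concern.** The amendment changed who could enter. An average below 3.5 h satisfies a definition of 3.5 h or less, so every version 1.0 entrant is a struggler, while version 2.0 entrants are a mixture of strugglers and others. Because the protocol itself treats early use as predictive, the two groups can be expected to differ in mean usage at 90 days.

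Protocol version is known at enrolment and cannot be affected by the assigned arm. A covariate of that kind can be adjusted for at almost no cost. Without it, the difference between cohorts goes into residual error. The single pooled estimate also averages an enriched and an unselected population in proportions fixed by the date of the amendment. The plan has no analysis that shows the two cohorts separately.

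**Working it through.** **1. The plan's own figure.** Inputs from Section 3.6: difference 0.8 h, SDs 2.5 (control) and 2.0 (test), 180/90, one-sided 0.025. The standard error is √(6.25/180 + 4.00/90) = 0.281 h. The unequal-variance t-test (noncentral t, Satterthwaite df 216.6) has 80.8% power. The smallest 2:1 design reaching 80% is 267 (178/89), close to the stated 270, and 270/0.9 = 300. The sample size reproduces.

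**2. Inputs that the documents do not give.** These are the share *p* randomised under version 1.0 and the gap *d* in mean usage between cohorts. I assume *p* = 20-50% and *d* = 1-2 h.

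**3. Variance explained by version.** Between-cohort variance is p(1−p)d², compared with the control-arm variance 2.5² = 6.25.

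| p | d (h) | p(1−p)d² | Share of 6.25 |
|---|---|---|---|
| 0.2 | 1 | 0.16 | 2.6% |
| 0.5 | 1 | 0.25 | 4.0% |
| 0.2 | 2 | 0.64 | 10.2% |
| 0.5 | 2 | 1.00 | 16.0% |

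**4. Why the range stops at 2 h.** Version 2.0 also admits strugglers. If a share *q* of its entrants are strugglers (assumption), a cohort gap *d* requires a struggler/non-struggler gap of d/(1−q), and hence a variance of q(1−q)[d/(1−q)]² within version 2.0 alone.
- d = 3 h: q = 0.4 needs a 5 h gap and gives 0.24 × 25 = 6.0; q = 0.5 needs 6 h and gives 0.25 × 36 = 9.0. The first is nearly all of 6.25 and the second exceeds it.
- d = 2 h: q = 0.4 gives 0.24 × 3.33² = 2.7; q = 0.5 gives 0.25 × 4² = 4.0. Both fit within 6.25, but 4.0 already equals the whole test-arm variance, so 2 h is an upper end.

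**5. Effect on power at 180/90.** Section 3.6 does not say whether 2.5/2.0 describe spread within a cohort or across the mixed population. The calculation in step 1 is repeated with p(1−p)d² added to both variances (within-cohort reading, term omitted) or subtracted from both (total reading, term included).

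| p | d (h) | Within-cohort SDs: power without term (80.8% with it) | Total SDs: power with term (80.8% without it) |
|---|---|---|---|
| 0.2 | 1 | 79.5% | 82.1% |
| 0.5 | 1 | 78.8% | 82.9% |
| 0.2 | 2 | 75.7% | 86.1% |
| 0.5 | 2 | 73.0% | 89.0% |

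On either reading the term gains about 1-2 percentage points for a 1 h gap and about 5-8 for a 2 h gap. Power falls below plan only on the within-cohort reading.

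**6. Bias and type I error.** In 20,000 simulated trials per setting (180/90, d = 2 h, p = 25% and 50%, same treatment effect in both cohorts, myAir left out), the mean error of the arm difference was under 0.005 h with or without the term. One-sided rejection under the null was 0.018 without the term and 0.017 with it, against a nominal 0.025. Both are below nominal because ANOVA pools the variances while the larger arm is the more variable: the pooled variance is (180 × 6.25 + 90 × 4)/270 = 5.5, giving a standard error of √(5.5 × (1/180 + 1/90)) = 0.303 h against the true 0.281 h. The empirical SD of the estimate was 0.30-0.31 h without the term and 0.28 h with it.

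**The case against.** The strongest objection is that no passage says anyone was randomised under version 1.0. The only evidence is one line of version history about superseded text, and Section 3.1 still describes enrolment as lying ahead. This stands, and it makes the point conditional. The 179 days between versions (about 26 weeks), set against a projected 16-week enrolment, make version 1.0 entrants plausible but do not show that there were any. The history line is used here only as evidence that eligibility changed, not as a conflict with the current text.

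Second, randomisation makes version independent of arm, so chance imbalance in version is ordinary sampling error. This also stands. At 200/100 a one-SD imbalance moves the unadjusted difference by d√[p(1−p)(1/200 + 1/100)], which is 0.05 h (p = 0.2, d = 1) to 0.12 h (p = 0.5, d = 2). That is already part of the unadjusted standard error and is not an additional error.

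Third, the planned struggler analyses address the characteristic on which the versions differ, and non-strugglers can only be version 2.0 entrants. This stands in part: readers would see something of how the effect varies with early use. But those analyses do not adjust the primary model, and the struggler group mixes entrants from both versions. Under version 2.0 the first three days of use may also follow randomisation, and Section 5.1 rewards successful nights on days 1, 2 and 3, so struggler status may itself respond to the intervention. Version cannot.

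Finally, Section 1 reports a significant association with adherence at 30 days. It gives no effect size for mean hours at 90 days, so the cohort gap remains an assumption.

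**Conclusion.** The point holds conditionally, as an improvement that costs almost nothing and not as an error that undermines the trial. If anyone was randomised under version 1.0, both Section 3.9 models omit a probably prognostic covariate fixed before randomisation. With 20-50% under version 1.0 and a 1-2 h cohort gap, both assumed, it would explain about 3-16% of the control-arm variance. If nobody was, the effect is nil.

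A reader might infer more than the documents support:
- That pooling biases the comparison of mean usage or inflates false positives. It does neither. If the effect differs between cohorts, the pooled estimate is a valid average over an unplanned mix.
- That the trial is underpowered. That follows only if 2.5/2.0 are within-cohort SDs, which Section 3.6 does not say.
- That a conclusion about unselected patients must rest on version 2.0 participants alone. That would shrink the sample, and nothing in the plan requires it.

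**What to change.** State in the report how many participants were randomised under each version. In Section 3.9, provided that at least one was randomised under version 1.0:

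- add protocol version at enrolment (1.0/2.0) as a factor in the primary ANOVA and in the adherence logistic model;
- report the arm difference in mean usage with a 95% CI separately by version, pre-specified as descriptive;
- keep the pooled ITT comparison as the primary conclusion.

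The change should be written down before arm-level usage data are examined. It costs one degree of freedom per model and one table. Version follows from the enrolment record, so no new data are needed. In the logistic model the adjusted odds ratio is conditional on version and need not equal the unadjusted one, so the text should say which is reported. If nobody was randomised under version 1.0, one sentence saying so closes the point.

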1 INTRODUCTION

Obstructive Sleep Apnea (OSA) is a condition characterized by the partial or complete collapse of the upper airway during sleep. OSA comprises a continuous spectrum of severity ranging from simple snoring and upper airway resistance through mild to severe symptomatic obstructive hypopnea and apnea. The prevalence of sleep disordered breathing in the adult population is 24% males and 9% for females¹. The prevalence of symptomatic OSA in the adult population has been estimated to be 4% in males and 2% in females¹. These patients demonstrate behavioral and neuropsychological consequences to varying degrees, including excessive daytime sleepiness, intellectual deterioration and depression². More serious consequences include arterial systemic hypertension, arterial pulmonary hypertension and heart disease³.

The treatment of choice for OSA is Positive Airway Pressure (PAP). PAP acts as a positive airway splint, delivering a fixed positive airway pressure to the upper airway via a tube and mask. Humidification is used during PAP therapy to improve comfort of the delivered air and alleviate nasal dryness/congestion.

Although PAP therapy is the gold standard treatment for OSA, adherence to treatment is often poor. CMS guidelines define adherence as 4 or more hours per night of therapy use on 70% of nights during a consecutive 30-day window within the first 90 days of setup⁴. Anywhere from 30 to 85% of patients will be non-adherent according to this definition of adherence, which can be explained, in part, by factors such as socioeconomic status, age, gender, severity of presenting symptoms, health values/beliefs, and social support⁵. Importantly, patients who immediately adopt therapy, within the first 3 days, are significantly more likely to be adherent at 30 days⁶, and patients' usage at 1 month is significantly predictive of adherence at 1 year⁷. Without sustained, long-term therapy adherence, patients are at risk of negative health outcomes including but not limited to cardiovascular disease, stroke, diabetes, and depression. This study tests whether a combined financial plus social incentive can help users new become adherent to PAP therapy.

Financial incentive schemes have demonstrated effectiveness in a wide range of behavior change efforts including physical activity⁸, smoking cessation⁹, glucose monitoring¹⁰, weight loss¹¹, and medication adherence¹². The primary mechanisms of action explaining the observed behavior change are loss aversion and timely reinforcement. Humans are strongly influenced by loss aversion, also known as the endowment effect, whereby the threat of losing something that has been endowed is a stronger motivator than the potential reward of gaining something not currently possessed. Timely reinforcement is also key, given that in order for learning to occur, the behavioral action and the subsequent reinforcement for doing said action must be closely coupled in time - otherwise it is difficult to associate the behavior with the reward.

Additionally, there is an abundance of evidence that social support is a critical component to successful health behavior change¹³; however, the specific test of social support

provision in this project is novel. Social currency (e.g., pictures, video) will be delivered to the participant at intervals (e.g., after a participant hits a streak of therapy use), as well as a weekly summary report of therapy use. Testing the social component is especially intriguing as this is a long-term cost-effective and scalable solution.

2 OBJECTIVES

Evaluate whether a digitally delivered monetary and social reward scheme can increase therapy usage and 90-day adherence. Adherence will be monitored using cloud-based technology in which data from each PAP device is automatically transmitted to a secure, HIPAA-compliant system (AirView).

3 METHODS AND MATERIALS

3.1 POPULATION/PARTICIPANT SELECTION

The intended population for the study are patients with a new diagnosis of OSA who have been prescribed a ResMed flow generator compatible with AirView. Participants will be recruited from the site's database.

Enrollment period for all participants is projected to be 16 weeks after IRB approval and enrollment commencement.

3.2 STUDY DESIGN

This is a prospective, randomized, two-arm, open-label study to evaluate effectiveness of applying financial and social incentives via a smartphone-based app in helping participants achieve adherence to therapy. Randomization will include an allocation ratio of 2:1 (control:treatment).

Two 'site to participant' contacts are required during this study. These contacts can either occur at the clinical site or remotely (e.g., by telephone). During the initial contact, their interest in the study and eligibility will be confirmed, then they will be consented, asked to complete the Baseline Questionnaire, and their demographic information will be collected on case report forms (CRFs).

Participants randomized to the intervention (Group B) will be provided with information and assistance in downloading Restful to their smartphone and registering with Wellth.

At the final contact (90 days), the participant will be asked to complete an End of Study Questionnaire and the investigative staff will collect PAP therapy data for the trial period and record it on CRFs. Participants in Group B will have access to the Restful app discontinued. This completes the participant's active participation in the study.

Daily usage data from AirView will be collected and transmitted electronically from usage initiation to 90 days, and then through 180 days.

Study data will be captured on CRFs. See **Appendix A** for the **Baseline and End of Study Questionnaires**. See **Appendix B** for **Participant Instructions** related to the study procedures and the Restful app.

